8.2 Discontinuation from the Study

The Investigator should consider the following when withdrawing a participant from the study:

- A participant may withdraw from the study at any time at his/her own request or may be withdrawn at any time at the discretion of the Investigator for safety, behavioral, or administrative reasons. If a participant withdraws from study drug for any reason, they may remain within the study if they continue to consent to do so.
- If the participant withdraws consent for disclosure of future information, UAB may retain and continue to use any data collected before such the withdrawal of consent.
- If a participant withdraws from the study, he/she may request destruction of any samples taken and not tested, and the Investigator must document this in the site study records.

8.3 Lost to Follow-up

A participant will be considered lost to follow-up if he/she repeatedly fails to return for scheduled visits and is unable to be contacted by the study site.

The following actions must be taken if a participant fails to return to the clinic for a required study visit:

- The site must attempt to contact the participant and reschedule the missed visit as soon as possible and counsel the participant on the importance of maintaining the assigned visit schedule and ascertain whether or not the participant wishes to and/or should continue in the study.
- In cases in which the participant is deemed lost to follow-up, the Investigator or designee must make every effort to regain contact with the participant (where possible, 3 telephone calls and mail a certified letter to the participant's last known mailing address. These contact attempts should be documented in the participant's file.
- Should the participant continue to be unreachable, he/she will be considered to have withdrawn from the study with a primary reason of lost to follow-up.

9.0 STUDY ASSESSMENTS AND PROCEDURES

- Study procedures and their timing are summarized in the SoA.
- Adherence to the study design requirements, including those specified in the SoA, is essential and required for study conduct.
- All screening evaluations must be completed and reviewed to confirm that potential participants meet all eligibility criteria. The Investigator will maintain a screening log to record details of all participants screened and to confirm eligibility or record reasons for screening failure, as applicable.
- Sample handling: Routine bloodwork and laboratory measurements used for safety monitoring and eligibility assessment (CMP, coagulation measurements, CBC, pregnancy testing, etc.) will be processed and measured using local laboratory. Samples (blood) used for PK or biomarker assessment will undergo initial processing at the local site but will be shipped to a central lab ([name]) at UAB for curation and analysis. The procedure is detailed in the MOP.
- Repeat or unscheduled samples may be taken for safety reasons or for technical issues with the samples.
- Biomarker samples (blood) will be stored for up to 60 months after the end of the study.

9.1 Key Screening Assessments

- SARS-CoV-2 PCR testing or SARS-CoV-2 antigen testing (routine diagnostic test used for diagnosis of current illness to be used, no additional test required). It is recognized this may have been performed in the period prior to the screening period.
- Laboratory testing performed for clinical management may be used for screening assessment if obtained within 3 days of planned randomization.
- EKG performed for clinical management may be used for screening assessment if obtained within 7 days of planned randomization.

9.2 Efficacy Assessments

9.2.1 Blood Biomarkers

Blood

Blood will be collected as per the SoA, and samples will be collected and processed as described by the MOP. Samples may be stored for a maximum of 60 months following the end of study at a facility selected by the investigators to enable further analysis of biomarker responses to alvelestat.

Blood Biomarkers of Efficacy Collected

- NETosis
 - cell-free DNA
 - citrullinated histone H3
 - Myeloperoxidase (MPO)-DNA complexes

- Neutrophil Elastase
 - Plasma desmosine/isodesmosine
- Inflammation
 - Absolute and percentage neutrophil count
 - Absolute and percentage lymphocyte count
 - Neutrophil-lymphocyte ratio [NLR] derived
 - C-Reactive protein
 - IL-1beta
 - IL-6
 - IL-8
 - TNF-alpha)
 - Procalcitonin
- Coagulopathy
 - D-dimer

In addition, samples will be stored and analysis may be performed on additional biomarker variants thought to play a role in neutrophil elastase–induced damage to evaluate their association with observed neutrophil activation responses to alvelestat.

9.2.2 $\text{SaO}_2/\text{FiO}_2$ (Oxygen saturation/fraction inspired oxygen)

The ratio of O_2 saturation to fraction inspired O_2 ($\text{SaO}_2/\text{FiO}_2$) is a reliable, non-invasive surrogate for $\text{PaO}_2/\text{FiO}_2$ and predictive for 3-day worsening in patients with COVID-19 infection ([Vultaggio et al 2020](#)). This will be collected at baseline and during the study as in the SoA, measured as per local standard operating procedures.

9.3 Clinical Outcome Efficacy Measurements

The following information will be recorded for the Clinical Efficacy Endpoint Assessments, including those in [9.3.1](#) and [9.3.2](#):

- Date of hospitalization and discharge
- Dates of admission to and discharge from ICU
- Date of death
- Daily respiratory support requirements (room air, oxygen by mask or prongs, high flow oxygen, non-invasive ventilation, Extracorporeal Membrane Oxygenation (ECMO), invasive mechanical ventilation (to complete the Disease Progression Endpoint Assessment))
- Organ support, vasopressors, renal replacement
- Limitation of activities of daily living (as required for the WHO 9-point ordinal scale)

9.3.1 Effect on disease progression recorded as participant status

- Alive and free of respiratory failure
- Alive with respiratory failure (need for high-flow oxygen, Extracorporeal Membrane Oxygenation (ECMO), non-invasive or invasive mechanical ventilation

9.3.2 WHO 9-Point Ordinal Scale

Each assessment will be recorded as a number in the CRF based on the status categories below. Where possible the timing of each assessment should be similar (i.e. morning or evening throughout)

0. Uninfected, no clinical or virological evidence of infection
1. Ambulatory, no limitation of activities
2. Ambulatory, limitation of activities
3. Hospitalized – mild disease, no oxygen therapy
4. Hospitalized – mild disease, oxygen by mask or nasal prongs
5. Hospitalized – severe disease, noninvasive ventilation or high flow oxygen
6. Hospitalized – severe disease, intubation and mechanical ventilation
7. Hospitalized – severe disease, ventilation and additional organ support – vasopressors, renal replacement therapy, extracorporeal membrane oxygenation
8. Death

9.4 Safety Assessments

Planned time points for all safety assessments are provided in the SoA. Daily safety and adverse event assessments may include data acquired from routine clinical care. SAEs only to be collected during screening. SAEs/AEs to be collected from Randomization to Day 60.

9.4.1 Physical Examinations

- A complete physical examination will include, at a minimum, assessments of the cardiovascular, respiratory, gastrointestinal, integumentary, and neurological systems. Height and weight will also be measured and recorded if possible, based on the clinical conditions.
- A brief physical examination will include, at a minimum, assessments of the lungs, heart, abdomen, and skin.
- Investigators should pay special attention to clinical signs related to COVID-19 disease.

9.4.2 Vital Signs

Vital signs will be measured in a semi-supine position after 5 minutes of rest and will include temperature, systolic and diastolic blood pressure, heart rate, respiratory rate, and pulse oximetry.

- Oral or tympanic temperature.
- Blood pressure and pulse measurements will be assessed with a completely automated device. Manual techniques will be used only if an automated device is not available.
- Blood pressure and pulse measurements should be preceded by at least 5 minutes of rest for the participant in a quiet setting without distractions (e.g., television, cell phones).

Electrocardiograms

- 12-lead EKG will be obtained as outlined in the SoA using an EKG machine that automatically calculates the heart rate and measures PR, QRS, QT, and QTc intervals where possible. Refer to [Section 8.1](#) for QTc withdrawal criteria and additional QTc readings that may be necessary.
- Single EKGs will be performed at all scheduled time points, with the exception of when a change from baseline occurs that meets drug discontinuation criteria ([Section 8.1](#)). In this situation, a triplicate measurement is required to confirm the finding and for discontinuation decisions.
- When a triplicate EKG is required, 3 consecutive EKG tracings should be taken in a 30-minute period with at least 5 minutes between each EKG.
- QTc value will be calculated using the Fridericia formula ($QTc=QT/3\sqrt{RR}$). Alternative may be used in discussion with PI.

9.4.3 Headache

A proactive query for headache will be made at Baseline, and at end of treatment as per SoA and graded by CTCAE criteria (Grade 0- No headache, Grade 1 Mild pain Grade 2-Moderate pain; limiting instrumental activities of daily living, Grade 3 Severe pain; limiting self-care activities of daily living).

9.4.4 Clinical Safety Laboratory Assessments

- Refer to [Appendix 2](#) for the list of clinical laboratory tests to be performed and to the SOA for the timing and frequency.
- The Investigator must review the laboratory report, document this review, and record any clinically relevant changes occurring during the study in the AE section of the CRF. The laboratory reports must be filed with the source documents. Clinically significant abnormal laboratory findings are those that are not associated with the underlying disease, unless judged by the Investigator to be more severe than expected for the participant's condition.

- All laboratory tests with values considered clinically significantly abnormal during participation in the study should be repeated until the values return to normal or baseline, with a frequency based on the judgement of the Investigator. If such values do not return to normal/baseline within a period of time judged reasonable by the Investigator, the etiology should be identified and recorded in the CRF.

The monitoring schedule proposed for a case of acute liver function abnormalities or worsening of a liver function abnormality is reported is listed in [Section 8.1](#) (Liver Test Abnormalities).

- Clinically significant liver function abnormalities should be reported as an AE/AESI.
- All protocol-required laboratory assessments, as defined in [Appendix 2](#), must be conducted in accordance with the SoA.

9.4.5 Data Monitoring

Safety will be regularly reviewed by the Principal Investigator or delegate.

9.5 Adverse Events

The definitions of an AE, SAE, SUSAR, and UP can be found in [Appendix 4](#).

An AE will be reported by the participant (or, when appropriate, by a caregiver, surrogate, or the participant's legally authorized representative).

The Investigator and any designees are responsible for detecting, documenting, and reporting events that meet the definition of an AE or SAE and remain responsible for following AEs that are serious, considered related to the study treatment or the study, or that caused the participant to discontinue the study treatment (see [Section 8.1](#)).

9.5.1 Time Period and Frequency for Collecting AE and SAE Information

All SAEs will be collected from the signing of the ICF until the follow-up visit at the time points specified in the SoA. SAEs/AEs will be collected from Baseline/Randomization to Day 60 and mortality to Day 90.

All SAEs will be recorded and reported to safety reporting group within 24 hours, as indicated in [Appendix 4](#).

The method of recording, evaluating, and assessing causality of AEs and SAEs and the procedures for completing and transmitting SAE reports are provided in [Appendix 4](#).

9.5.2 Follow-up of an AE and/or SAE

After the initial AE/SAE report, the Investigator is required to proactively follow each participant at subsequent visits/contacts. All SAEs and non-serious AESIs (as defined in

Section 9.5.3), will be followed until resolution, until stabilization, until the event is otherwise explained, or until the participant is lost to follow-up (as defined in Section 8.3). Further information on follow-up procedures is given in [Appendix 4](#).

9.5.3 Adverse Events of Special Interest

Some AEs, regardless of their severity or outcome, will be expedited due to the relevance for subject safety or study treatment safety profile. These events should be reported to safety reporting group within 24 hours, as indicated in [Appendix 4](#). The AESIs for alvelestat are:

- Liver function abnormalities defined as:
 - a) Any occurrence of (i) ALT or AST elevations $>5 \times$ ULN or (ii) ALT or AST $>3 \times$ ULN and total bilirubin $>2 \times$ ULN or INR >1.5 or the appearance of worsening fatigue, nausea, vomiting, RUQ pain/tenderness, fever, rash, or eosinophilia.
 - b) Any occurrence of $<5 \times$ ULN or ALT or AST $<3 \times$ ULN and total bilirubin $<2 \times$ ULN where the tests have been repeated within 48 to 72 hours and the elevation confirmed on at least 2 separate occasions.

For participant safety and to ensure that the hepatotoxic potential of the study treatment to be determined, a standardized procedure for identification, monitoring, and evaluation of liver events must be followed as outlined in [Section 9.4.4](#) and [Section 8.1](#).

- EKG

If a study subject experiences any of the following cardiovascular events, the event should be reported immediately as an AESI and the study treatment discontinued:

- a) Absolute QTcF >500 ms or >60 ms increase from baseline.
- b) Any clinically significant cardiac abnormality on EKG.
- Infection

Any new infection that requires the use of systemic antimicrobial treatment (antibiotics, anti-viral, anti-fungal, or anti-mycobacterial) should be investigated with clinically relevant diagnostic tests.

- Neutropenia

Absolute neutrophil count less than or equal to 500 per μ L on 2 consecutive repeat tests within 48 to 72 hours.

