- Any elevation in ALT or AST with clinical hepatitis: ALT or AST >ULN and the appearance of worsening fatigue, nausea, vomiting, right upper quadrant pain/tenderness, fever, rash, or eosinophilia
- Alkaline phosphatase >2x ULN and direct bilirubin >2 x ULN

4) When the following hepatic adverse events are met, study treatment **MUST** be discontinued, the study PI be informed, and further steps discussed:

- Regardless of the magnitude of the transaminase elevation, if the bilirubin is elevated (any level) in addition to the presence of signs and symptom(s) such as rash, eosinophilia, nausea, vomiting, or right upper quadrant pain
- INR ≥ 1.5 (unless due to therapeutic anti-coagulant use) and TB ≥ 2.5 x ULN, irrespective of the magnitude of ALT or AST elevation
- TB elevation ≥ 2.5 x ULN, and ALP ≥ 2.5 x ULN for cholestatic liver injury.

For each scenario, initiate potential DILI evaluation for alternative etiologies and consider a hepatology consult. Liver biopsy should be considered for DILI. The complete liver profile including PT/INR must be repeated within 48-72 hours after first abnormal value is obtained. Follow the patient until laboratory parameters stabilize or normalize. Study medication can be restarted only if an alternative etiology is “definitively” identified and liver tests have returned to baseline. Testing for alternative etiologies can include serology tests (hepatitis A, hepatitis B, hepatitis C, Cytomegalovirus (CMV), Epstein-Barr Virus (EBV), Herpes Simplex Virus (HSV), varicella zoster virus (VZV), parvovirus, toxoplasmosis), imaging, and pathology assessments (creatinine phosphokinase, clotting) as appropriate to the clinical situation.

Clinically significant liver function abnormalities should be reported as an AE/AESI.

EKG Abnormalities

If a clinically significant finding is identified (including but not limited to changes from baseline in QTcF after enrolment), the Investigator or qualified designee will determine if the participant can continue in the study and if any change in participant management is needed. This review of the EKG printed at the time of collection must be documented. Any new clinically relevant finding should be reported as an AE.

When the following EKG change conditions are met, study treatment **MUST** be discontinued, the study PI informed, and further steps discussed:

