- Absolute QTcF >500 ms or >60 ms increase from baseline as confirmed with 3 consecutive EKGs taken in a 30-minute period with at least 5 minutes between each EKG. The mean of the 3 EKGs will be used for decision making.

Acute Kidney Injury (AKI)

Alvelestat is predominantly renally excreted and the effect of acute kidney failure on PK is unknown. Participants who develop AKI requiring dialysis or hemofiltration must have study drug discontinued.

Other Laboratory Parameters

Study treatment **MUST** be discontinued if the following laboratory parameters criteria are met:

- Absolute neutrophil count less than or equal to $0.5 \times 10^9/L$ on 2 consecutive repeat tests within 48 to 72 hours.

Other

Study treatment **MUST** be discontinued if the following other criteria are met:

- Significant safety issues (as judged by the Investigator). This includes AEs considered unacceptable by the patient and/or the Investigator
- Any other protocol deviation that results in a significant risk to subject's safety
- Pregnancy as confirmed by positive urine test at any time during the study
- Withdrawal of informed consent.
- Progression to intubation/mechanical ventilation or other circumstance where continued administration of study drug tablets by the oral route is not possible.

Participants may voluntarily discontinue investigational treatment for any reason at any time. Participant decision on discontinuation of study treatment does not imply an automatic withdrawal from the study.

Refer to the Schedule of Assessments (SoA) for data to be collected at the time of treatment discontinuation (EoT) and follow-up and for any further evaluations that need to be completed.

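### Protocol 9.5.3 and 8.1 differ on when an EKG finding stops study treatment and when it is an AESI, and two primary safety counts depend on the answer

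*Protocol*

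**What the plan says.** Protocol 9.5.3, in its EKG item, lists two triggers: (a) "Absolute QTcF >500 ms or >60 ms increase from baseline" and (b) "Any clinically significant cardiac abnormality on EKG". For either one, "the event should be reported immediately as an AESI and the study treatment discontinued". The item mentions no repeat tracing.

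Protocol 8.1, under EKG Abnormalities, covers the same ground differently. For clinically significant findings in general, "the Investigator or qualified designee will determine if the participant can continue in the study", and a new relevant finding is to be reported as an AE. Stopping treatment is mandatory at the same QTcF limits as in 9.5.3(a), but "as confirmed with 3 consecutive EKGs taken in a 30-minute period with at least 5 minutes between each EKG". The section adds: "The mean of the 3 EKGs will be used for decision making".

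Protocol 9.4.2 makes scheduled EKGs single tracings. Where a change reaches the discontinuation criteria, "a triplicate measurement is required to confirm the finding and for discontinuation decisions".

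The primary endpoints (Protocol synopsis and section 4.0; SAP Table 3) include AESIs, with the EKG component named only as corrected QT interval, and the number and percentage discontinuing alvelestat. Protocol 5.8 treats clinically significant EKG changes as an AESI, and Protocol 10.3.1 tabulates EKG events. SAP 8.3 gives neither a QTcF confirmation rule nor a definition of a countable EKG event.

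**The concern.** Two sections of the current protocol instruct the site on the same EKG event, and the instructions do not match. One attaches a stop and an AESI report to the finding. The other attaches a confirmation step or the investigator's decision, and an AE report.

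This is a safety instruction for a risk that the protocol itself singles out: section 5.8 relies on EKG monitoring, discontinuation criteria and AESI status because of the QTc changes seen in dogs. It is also a definition problem for the analysis. Both the AESI tally and the discontinuation tally are primary components, and the SAP adds no rule that would settle which events count.

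**Working it through.** The point rests on comparing texts. The plan gives no figure to reproduce.

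**Step 1. The instructions side by side.**

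| Situation | 9.5.3 | 8.1 | 9.4.2 |
|---|---|---|---|
| QTcF beyond the limits | Stop and AESI; no confirmation stated | Stop mandatory once confirmed by three EKGs, on their mean | Triplicate needed to confirm and to decide |
| Other clinically significant EKG finding | Stop and AESI | Investigator or designee decides; AE report | No rule |

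The mean and the investigator's decision on continuing come from 8.1 alone. Section 9.4.2 contributes only the triplicate.

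**Step 2. What happens to a patient under each section.**

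- *Scheduled tracing beyond a QTcF limit, triplicate mean also beyond it.* Both sections stop treatment. There is no conflict on stopping.
- *Scheduled tracing beyond a limit, triplicate mean within it.* Read literally, 9.5.3(a) gives a stop and an AESI. Under 8.1 and 9.4.2 the mandatory stop is not triggered, and AESI status is left open.
- *Clinically significant finding other than QTcF.* Section 9.5.3(b) gives a stop and an AESI. Section 8.1 gives a decision by the investigator and an AE.

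The second and third cases can be recorded differently depending on the section followed.

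**Step 3. Is the lack of a confirmation step in 9.5.3(a) just brevity?** The neutropenia item in the same section writes its repeat testing into the definition ("on 2 consecutive repeat tests within 48 to 72 hours"). Liver item (b) also requires repeat testing, and the liver text refers the reader to 8.1. The EKG item does neither, so nothing in it points to the triplicate.

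**Step 4. Which events reach the endpoint?** The third case is an AESI under 9.5.3(b) and 5.8, and would fall under the EKG events of 10.3.1. The primary endpoint names only corrected QT interval. Whether such an event is counted is therefore undefined.

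**Step 5. Weight of one patient.** One reclassified patient shifts an arm's percentage by 100/n points.

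- Protocol 5.2, 10 on alvelestat: 100/10 = 10.0 points.
- Protocol 5.2, 5 on control: 100/5 = 20.0 points.
- SAP Table 1, 7 to 8 per arm: 100/8 = 12.5 to 100/7 = 14.3 points.

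The protocol (2:1) and the SAP (1:1) disagree on allocation, so both sets are shown. The denominators assume that every randomized patient is dosed and so enters the Safety Set.

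**The case against.** The strongest reply concerns QTcF. Section 9.4.2 is worded generally: whenever a change meets the discontinuation criteria, a triplicate confirms it and informs the decision. A site could read 9.5.3(a) as naming the event and 8.1 with 9.4.2 as saying how it is established. Three tracings within 30 minutes are compatible with prompt reporting, and 8.1 says must where 9.5.3 says should. A reader might infer that 9.5.3 expressly stops treatment on one tracing, or that the QTcF instructions can never both be obeyed. The documents do not support either statement: 9.5.3 does not give the number of tracings, and the harmonised reading is available. What remains is that 9.5.3 does not point to that reading, although its neighbouring items do state repeat tests.

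On other findings, 8.1 speaks of continuing in the study, which the protocol elsewhere separates from continuing on treatment, and calling an abnormality clinically significant is itself a judgement. Both are fair. However, the sentence stands under the heading on discontinuing study treatment and also covers changes in the participant's management, and 8.1 asks for an AE where 9.5.3(b) asks for an AESI. The conflict stands.

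The effect on discontinuations may also be small. After Day 1, few on-treatment EKGs are scheduled: one on any of Days 3 to 5, and one at Day 10 for those who extend. A finding on the last dosing day leaves little treatment to stop. That limits the discontinuation count but not the AESI count.

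**Conclusion.** The inconsistency is real and lies in the operative text. It is firm for clinically significant EKG findings other than QTcF, where 9.5.3(b) and 8.1 differ on both the action and the reporting class. For QTcF it is weaker: a confirmation step is stated in 8.1 and 9.4.2, is absent from 9.5.3, and can be harmonised only by interpretation.

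The AESI count and the number discontinuing alvelestat can therefore differ with the section followed. One patient is worth 10 points in the protocol's alvelestat arm, or 12.5 to 14.3 points under the SAP's allocation. This is the weight of a single reclassification, not a forecast. The documents give neither a within-patient QTcF variability nor an expected QTcF change in these patients, and Protocol 5.8 reports no clear treatment effect on EKG in completed studies, so no frequency is claimed.

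A reader might also infer that every event under 9.5.3(b) alters the primary QT AESI count. That does not follow, because the endpoint names only corrected QT interval; whether such events count is the undefined part. The point deserves correction, but the trial is an exploratory pilot without a powered comparison, and no formal inference depends on it.

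**What to change.** Protocol 8.1 (EKG Abnormalities), 9.4.2 (Electrocardiograms) and 9.5.3 (EKG item) must be reconciled so that they agree on when an EKG finding leads to discontinuation of study treatment and when it is an AESI. The two definitions need not be identical, but each should be stated once and cross-referenced. Which clinical rule is right is for the sponsor and investigators to decide, and this review takes no position.

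The SAP should then count EKG and QT AESIs by the reconciled definition, and state whether EKG events other than QT prolongation belong to the primary AESI component. The endpoint wording in the Protocol synopsis, section 4.0 and SAP Table 3 should match.

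The cost is a wording amendment to the protocol and a definition or table footnote in the SAP. No added patients or assessments follow from aligning the text itself.
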